### Summary

We will pre-screen potential participants over the phone to minimize the invitation to non-eligible participants. During the screening visit, we will screen patients for eligibility. Patients will then arrive for their study Day # 2(Baseline), when they will get blood draws (optional), complete questionnaires and undergo TMS-EEG. Patients will come to our inpatient psychiatric hospital facility on the another day (Day # 3) , where they will be given ketamine by the study nurse. During the infusion, patients will be asked constantly about "how they feel" and will be monitored continuously from psychiatric nurse and the attending Anesthesiologist. EKG and pulse-oximetry will be monitored throughout the procedure to check for hemodynamic changes. After the completion of 40 min infusion, patients will rest for two – four hours under the observation of clinical nurse and, reassessed again by psychiatrists at 2 hours after infusion. Patients may be undergoing EEG/ASSR at 10minutes, 40 minutes and at 4 hours after infusion and blood tests after infusion(40 minutes) and 2-4 hours after infusion. Patient will then

have undergo TMS-EEG & EMG at 4 hours. Patient will be discharged to a responsible adult who will accompany the patient home. Patients will be invited again for day #4 (24 hours after infusion), where they will have to complete TMS-EEG & EMG, EEG/ASSR(optional) and blood tests(optional). They will be invited again for just TMS 7 days after infusion. Patients may be contacted every day after the infusion by telephone to check on their physical and mood status and will be scheduled for a clinical visit with the psychiatrists on days 1, 4, and 7 for a follow up assessment of mental state.

### **Study Population**

We will enroll 20 patients with Treatment Resistant Depression (TRD) in this study. Participants will be male and female adults, aged 18-60 years, who meet the criteria for TRD. Participants will be recruited without regard to race, religion or ethnicity. Children will NOT be included in this research. Children younger than 18 are excluded as the incidence of TRD is relatively small in individuals less than 18 years old and because the safety and efficacy of the proposed study medication and treatment should be established in adults first, before conducting this type of treatment research in children. No other special classes of vulnerable individuals will be included. Participants will be recruited through flyers and clinic referrals in the Houston area.

We anticipate recruiting equal numbers of male and female patient subjects. Men and women of all ethnic backgrounds will be recruited to participate. It is anticipated that the subject demographic profile will closely mirror the larger population of individuals with TRD from which they are recruited. We will do so by distributing flyers in neighborhoods known to have a high minority population.

Selection Criteria for individuals:

#### **Inclusion criteria –**

1. Be between 18-60 years of age
2. Meet criteria for TRD (defined as two or more unsuccessful trials of antidepressants at an adequate dose for at least 4 weeks)

#### **Exclusion criteria –**

1. Diagnosed with intellectual disability, eg. Mental retardation, neurodegenerative diseases, eg. Early onset neurocognitive disturbances such as frontotemporal dementia or behavioral disorders, eg. adult onset Attention Deficit Hyperactivity Disorder
2. Diagnosed with Bipolar Disorder (BD)
3. Diagnosed with personality disorders
4. Previously or currently diagnosed with psychosis (schizoaffective disorder –SAD) or schizophrenia – SCZ)
5. Current major medical problems that affect brain anatomy, neurochemistry, or function, e.g., obstructive sleep apnea requiring Continuous Positive Airway Pressure (CPAP), liver insufficiency, kidney insufficiency, cardiovascular problems, systemic infections, cancer, auto-immune diseases, and any brain disorder (seizure disorder, stroke, dementia, degenerative neurologic diseases); history of any brain diseases, including seizures, stroke, meningitis, encephalitis, dementia, degenerative brain diseases, and head injury with loss of consciousness for any period of time
6. Diagnosed specifically with a cardiovascular disorders such as "uncontrolled" hypertension or diastolic BP over 100, Arrhythmias, Chronic Heart Failure, Myocardial Infarction (MI) or suffering from Chronic Obstructive Pulmonary Disease (COPD) or asthma. Cardiac clearance prior to enrolling in the study and medical records from physician will be required per patient's PCP
7. Patients with increased risk of laryngospasm, active upper respiratory infections, respiratory depression, increased intracranial pressure, hyperthyroidism, or porphyria
8. Current substance abuse or dependence. Only patients who achieved stable, full remission for at least 6 months will be included
9. Pregnancy or Breast feeding. All female in reproductive age will undergo pregnancy tests. Female participants will be required to provide evidence of use of contraceptives during the course of the study,
10. Unable to understand the design and requirements of the study

11. Unable to sign the informed consent for any reason.

**Sources of Materials:** All participants will provide demographic, health and psychiatric history information obtained at screening, and electro-physiological (e.g. EMG-TMS, blood pressure) data obtained during the study sessions. We will also obtain urine at all study sessions to ascertain drug and alcohol use and (in women) pregnancy status. All data collected on paper forms will be stored in locked cabinets, while electronic data is stored on our secure password protected server (maintained by the UTHealth Medical School Information Technology Department). All electronic records will identify study participants only by a study code, and the electronic file linking codes to individual identifiers will be destroyed once data collection is complete.

## Potential Risks

### For all participants:

1. *Diagnostic procedures and questionnaires:* Some of the questions asked during the screening may be considered sensitive information, including drug use history and psychiatric history. Answering these questions may be psychologically discomforting to some subjects. There are also risks associated with loss of confidentiality.

2. *Psychophysiological monitoring:* We will monitor psychophysiological responses using conductive electrodes attached to the skin of participants with an adhesive. There may be mild discomfort or irritation to the participant's skin as a result of cleaning the sites to apply the sensors, but this should be transient. Approximately half of individuals experience slight stinging/irritation lasting around 15 min. A few individuals experience red marks at the site of application that can last up to one day after the application. A very small number of participants with particularly sensitive skin may experience marks that last longer (up to two to three days). All equipment will be appropriately grounded and shielded, and stimulus equipment will be optically isolated from the participant making any electrical hazard to the participant extremely unlikely. All surfaces in contact with the participants' skin are disposable, and all equipment will be thoroughly cleaned between sessions to make risk of infection also unlikely.

*Neurophysiology Testing-* Participants may experience some mild discomfort during tasks involving presentation of auditory stimuli.

*EEG-*The EEG (electroencephalograph) is a non-invasive procedure which may cause skin irritation from the placement of recording electrodes in less than 1% of people. Itchiness of scalp or redness because of electrode gel could result and is the same amount of risk as any saline solution. The EEG is administered by trained research staff and can be stopped at any time if the subject becomes uncomfortable.

*TMS-* The side effects with TMS are very rare. The most common side effects include headaches and ringing in the ears (earplugs are always worn to prevent this). TMS side effects also include a small risk of seizure and convulsion. This is a very rare complication; the reported risk is less than 1 in 1000 for repetitive TMS and even lower in physically healthy patients. This risk is lowered in this protocol as we will not be doing repetitive TMS.

3. *Study Medication.* Side effects associated with ketamine injection are rare and, if any, of transient duration. The most commonly reported side effects during a 4 hour period after infusion include feeling strange or unreal (58.3%), abnormal sensations (54.2%), blurred vision (50.0%), feeling drowsy or sleepy (48.5%) and headaches (30-40%). Based on previous evidence, we do not expect ketamine to impair cognitive functions such as memory, attention or language. If patients are currently taking certain medications on a daily basis within 24 hours prior to and / or after receiving ketamine, they will not be able to take these medication(s) while receiving a ketamine infusion without clearance or approval of the physicians involved in administering ketamine. Medications include: Sedatives (e.g., clonazepam, lorazepam, alprazolam); Antibiotics (e.g., azithromycin, clarithromycin); Antifungal agents (e.g., ketoconazole); Tramadol. This is due to concerns for potential increased sedation or trouble breathing. The risk of addiction to ketamine for a single –dose study is very rare.

## **Adequacy of protection against risks**

**Recruitment and Informed Consent:** Participants will be self-referred in response to various study advertisements via flyers. Individuals who call for information will be given a brief description of the study. Those interested will then be asked to answer questions about their disease status. A trained research assistant will conduct this telephone-screening interview. Eligible subjects will be scheduled for an in-person screening visit at the BSBB.

Once eligible for the study, they will be invited for study Day# 1, which will begin with the presentation of the informed consent form. The consent form will detail the requirements of study participation (e.g., # of visits, type of data collected, time commitment, etc.) Subjects will be told that the purpose of the study is to evaluate neurophysiological measures to study the effect of ketamine on TRD. Subjects will be informed that they will have to attend a total of five visits (screening and four study visits). Other information on the consent form will include a full description of study requirements, reimbursement, risks, benefits, alternatives, and the role of the local IRB. All questions will be answered before written consent is requested. Informed consent will be obtained only by the PI or a trained senior member of the staff (e.g. study coordinator).

The research protocol, consent form, and all assessment/advertising materials will be reviewed and approved by the Committee for the Protection of Human Subjects (CPHS) at UTH.

### **Protections against risk**

1. Risks related to diagnostic procedures/questionnaires: As noted above, the primary risks related to these procedures are participant discomfort and loss of confidentiality. Regarding participant discomfort, we will make clear that we ask for this sensitive information as part of the consent process. Further, while subjects may be uncomfortable reporting these issues, the risks of serious sequelae are extremely low. Regarding confidentiality, we have rigorous procedures in place to ensure confidentiality of data, including locked cabinets for confidential files, participant coding, secure computer systems, and rigorous training of personnel. Computer systems are secure and strictly monitored by University IT staff. Laboratory staffers are trained in confidentiality of participant information. No information is allowed to leave the lab or to be accessed by a computer outside of the university's secure computer system, and all data are further protected by permissions and passwords given only to necessary research personnel. No information will be published in a form in which the participant can be identified. We will also obtain a Certificate of Confidentiality for this study to provide additional protection for sensitive information.
2. Risks related to psychophysiological monitoring: As noted above, precautions are taken to make electrical hazards from equipment unlikely, including correct grounding and optical isolation of the participant. Disease hazards are minimized through disposable electrode collars and thorough cleaning processes. Mild, transient skin irritation from cleaning procedures is common (as described above), but the possibility of more serious skin irritation will be minimized by asking participants about previous allergic reactions to rubbing alcohol or exfoliants and rigorous training in correct skin cleaning procedures for research assistants.
3. Electroencephalography (EEG): The EEG is administered by trained research staff and can be stopped at any time if the subject becomes uncomfortable.
4. Transcranial Magnetic Stimulation (TMS): Earplugs are always worn to prevent any headaches or ringing in ears caused by TMS noise. In this protocol, since it will not be repetitive TMS, the risk is very rare.
5. Neurophysiology Testing: Patients may stop at any time if they experience any discomfort during tasks involving presentation of emotional pictures or auditory stimuli. The decibel levels of the auditory task will be checked before start of the study and will not fluctuate significantly through the study.
6. Risks related to study medication: The following procedures will be taken to safeguard against adverse medication events: (1) careful initial intake evaluation to determine eligibility based on inclusion/exclusion

criteria; (2) thorough physical evaluation prior to infusion, consisting of physical examination, standard laboratory tests, electrocardiogram, urine toxicology screen, pregnancy test and vital signs; (3) Monitoring of concomitant illicit drug use at each visit with self-report, urine and/or breath testing; (4) Review of medication response, adverse events, and medication compliance with the study nurse; (5) Regular evaluation of all medical information. In the event that contraindicated medical conditions and/or other serious adverse symptoms arise after initiation of the medication, medication will be discontinued and the subject will be examined.

7. **Risks related to alternative treatments:** As noted above, we believe that our therapeutic interventions provide treatment that is considerably superior to most, if not all treatment opportunities in the community. Nevertheless, we will refer patients to other facilities upon request or when required by other circumstances. We will also conduct regular literature searches on alternative treatments, and in the event that an alternative treatment emerges with clearly superior efficacy, we would suspend the current study and provide all participants with referrals for this alternative treatment.
8. **Study withdrawal:** The research study and participation is completely voluntary. Participants can withdraw from the study at any time without giving a reason and without any consequence. A decision not to take part or to stop being a part of the research project will not change the services available to them from the UTHSC-H, Department of Psychiatry or the HCPC. The investigators could stop participation if an unfavorable or unexpected reaction is noticed.
9. **Unanticipated Hospitalizations:** If a patient needs to be hospitalized for worsening of symptoms or for their own personal safety, they will be removed from their study participation and their study treatment will end at that time.
10. **Risks of blood draw:** There are minimal risks involved in having the blood draw for the study. The blood sample will be drawn from a peripheral vein, by a trained staff person. The risks involved are related to local bruising but these will be minimized by the use of trained personnel.

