7. **Young Mania Rating Scale (YMRS):** This is a well-established clinical severity rating scale for manic symptoms that has adequate inter-rater reliability and internal consistency (Young et al., 1978). Frequency: Before the start of the study and at 4 hours, 24 hours and 7 days after infusion. (Changed based on the PI).
8. **Positive and Negative Affect Schedule (PANAS):** the PANAS comprises two mood scales, one that measures positive affect (PA) and the other which measures negative affect (NA). Used as a psychometric scale, the PANAS can show relations between positive and negative affect with personality stats and traits. Ten descriptors are used for each PA scale and NA to define their meanings. Participants in the PANAS are required to respond to a 20-item test using 5-point scale that ranges from very slightly or not at all (1) to extremely (5). This scale may be administered prior to and following each infusion to assess acute changes in mood. Frequency: Before the start of the study and at 4 hours, 24 hours and 7 days after infusion. (Changed based on the PI).
9. **The World Health Organization Quality of Life (WHOQOL)-Brief :** this scale is patient-reported and measures the degree of enjoyment and satisfaction experienced by subjects in various areas of daily functioning (*Endicott*

*et al.*, 1993). Frequency: Before the start of the study and at 4 hours and 24 hours after infusion. (Changed based on the PI).

**10. Hamilton Depression Rating Scale (HDRS):** a multiple item questionnaire used to provide an indication of depression, and as a guide to evaluate recovery. Frequency: Before the start of the study and at 4 hours, 24 hours and 7 days after infusion. (Changed based on the PI).

**11. Hollingshead Socioeconomic Status:** This scale is patient-reported and indication of socioeconomic status. Frequency: At the discretion of the PI.

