### **Statistics**

Normality assumptions for continuous variables will be examined. Where appropriate, outliers will be winsorised and log, square root or reciprocal transformations applied to achieve normality if appropriate. If normality cannot not been achieved, either untransformed or dichotomized scores were used. Baseline characteristics will be compared between responders and non-responders with the Mann-Whitney U test for continuous variables and the chi-square test for categorical variables. Changes between two time-points for continuous variables were tested with paired t tests, and associations between continuous variables will be quantified with the Spearman correlation coefficient. Random effects models will be performed to quantify changes in clinical score and its component items over time and to compare temporal differences between eventual responders and non-responders. Splines will be used to determine differences in the pattern of response over time among all patients and to identify the time at which there was no additional improvement in depressive symptoms. Additionally, the relationship between response status between baseline and end of study calculating sensitivity, specificity, and positive and negative predictive values will be reported. Time to relapse for patients who met response criteria at end point will be estimated with the Kaplan-Meier method. Analyses will be performed with IBM SPSS Statistics (version 19; SPSS, Chicago, Illinois) and SAS (version 9.2; SAS, Cary, North Carolina).

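### Ending participation when a patient is hospitalised for worsening, with no rule for the missing day-7 scores, could overstate day-7 improvement and response

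*Combined protocol and SAP*

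**What the plan says.** In the Combined protocol and SAP, item 9 of Protections against risk (Unanticipated Hospitalizations) sets the trigger: "If a patient needs to be hospitalized for worsening of symptoms or for their own personal safety". The consequence is that "they will be removed from their study participation and their study treatment will end at that time".

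Clinical assessment schedules the HDRS, and likewise the MADRS, "Before the start of the study and at 4 hours, 24 hours and 7 days after infusion", subject to change by the PI. The visit schedule under Summary contains one infusion. After an SAE, the Safety monitoring plan provides for medical follow-up; it does not mention rating scales.

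The Statistics section lists several analyses that bear on this:
- "Changes between two time-points for continuous variables were tested with paired t tests"
- "Random effects models will be performed to quantify changes in clinical score and its component items over time", together with a comparison of eventual responders and non-responders over time
- sensitivity, specificity and predictive values for "the relationship between response status between baseline and end of study"
- "Time to relapse for patients who met response criteria at end point will be estimated with the Kaplan-Meier method"

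It gives no analysis set, no numerical definition of response, no rule for missing data and no statement of how a removed patient counts. Power Analysis treats attrition only as a loss of sample size.

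**The concern.** The trigger for removal is closely tied to the outcome being measured. With a single infusion already given, little treatment is left to end, so removal mainly stops data collection. The patients whose day-7 scores would go missing are then likely to be among the worst.

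A paired comparison of baseline with day 7 cannot use a patient who has no day-7 score. A responder analysis has nothing with which to classify that patient. Losses of this kind push the apparent result towards benefit, and an open-label study without a control arm has no comparison that would reveal it.

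The biomarker work is exposed too. The Blood Tests section correlates HDRS reduction with expression and methylation markers and compares responders with non-responders, so losing clear non-responders removes informative patients. Such hospitalisations are foreseeable: the protocol wrote a rule for them, suicidality is not among the listed exclusions, and the Columbia suicide scale is among the assessments.

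**Working it through.** **The plan's own figures.** Power Analysis gives d = 0.9, two-sided alpha 0.05, N = 15, 95% power, and 20 enrolled to allow for 20% attrition.
- Within-subject normal approximation: Φ(0.9 × √15 − 1.96) = Φ(1.526), about 93.7%, close to the stated 95%. The exact two-sided paired t test gives 90.0%.
- Attrition: 20 × (1 − 0.20) = 16, which covers 15.

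So attrition enters the plan only as a smaller n. Nothing addresses who is lost.

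**Inputs for the response rate.** The number removed between infusion and day 7, h, is not given. I assume a range of 0 to 4 of 20. The upper end uses the whole 20% attrition allowance and is an extreme ceiling. Two illustrative day-7 rates come from Background Information: 35%, which is 7 of 20, and 21/47 = 44.7%, which is nearest to 9 of 20 (45%). Removed patients are assumed to be true non-responders.

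Completer rate = responders / (20 − h). The rate with removed patients counted as non-responders is responders / 20. The inflation factor is 20 / (20 − h).

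| h | 7 responders | 9 responders | Factor |
|---|---|---|---|
| 0 | 7/20 = 35.0% | 9/20 = 45.0% | 1.00 |
| 1 | 7/19 = 36.8% | 9/19 = 47.4% | 1.05 |
| 2 | 7/18 = 38.9% | 9/18 = 50.0% | 1.11 |
| 3 | 7/17 = 41.2% | 9/17 = 52.9% | 1.18 |
| 4 | 7/16 = 43.8% | 9/16 = 56.3% | 1.25 |

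**Mean change, complete pairs.** Overstatement = (h/20) × (mean improvement of those kept − mean improvement of those removed). Assume that those kept improve by 0.9 SD.
- Those removed do not change: 1/20 × 0.9 = 0.045 SD, up to 4/20 × 0.9 = 0.18 SD.
- Those removed worsen by 0.9 SD: 1/20 × 1.8 = 0.09 SD, up to 4/20 × 1.8 = 0.36 SD.

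On the HDRS scale, with assumed values: if the true mean change is −8 and 2 of 20 worsen by 5, the completer mean is (20 × (−8) − 2 × 5)/18 = −170/18 = −9.4.

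**What the random effects model would do.** A large-sample simulation assumed a true day-7 change of 0.9 SD, a correlation of 0.6 between 24-hour and day-7 change, and removal of the worst 5% to 20%. A regression estimate that assumes data missing at random stood in for the random effects model.

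| Removal depends on | Complete pairs | Model |
|---|---|---|
| observed 24-hour score | 0.97 to 1.11 SD | 0.90 SD |
| unseen day-7 state | 1.01 to 1.25 SD | 0.97 to 1.16 SD |

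The scheduled depression ratings jump from 24 hours to day 7. Six of the seven days therefore fall after the last score that the model could use for a removed patient, and the favourable first row cannot be taken for granted.

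**The case against.** The strongest defence has four parts.

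**The plan already has a longitudinal model.** Random effects models are named for the clinical score, while paired t tests are listed generically for continuous variables. The model can keep a removed patient's baseline, 4-hour and 24-hour scores. This stands, and it may remove the bias in the mean. It does not repair the paired tests, and it does not give a removed patient a responder status.

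**The text does not leave anyone out of the responder analyses.** A reader might infer that removed patients are omitted. The Statistics section is silent, and counting them as non-responders would be equally compatible with it. The defect is that the choice is left open until the data are seen.

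**The relapse analysis need not censor these patients.** A reader might infer that they are censored in the Kaplan-Meier analysis at the moment they worsen. That analysis is limited to patients who respond at end point, a term that is not defined. If it means day 7, someone removed earlier would never enter. If it means an earlier time, the patient already has an end-point status. The censoring reading and the missing-responder reading cannot both hold under one definition.

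**The clinical scores are not the main target.** The primary goal is cortical neurophysiology, power rests on ASSR and motor threshold, and no response rate is named as an estimate. The sample is also imprecise: the exact 95% interval for 9/20 runs from about 23% to 68%, far wider than the shift from one removal. This lowers the priority. It does not remove the problem, because responder status and HDRS reduction feed the biomarker and predictive-value analyses.

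**Conclusion.** The concern holds in conditional form. If a patient is hospitalised for worsening between infusion and day 7, the stated rules drop that patient from the day-7 paired tests and leave the end-of-study response status without a score. The resulting error favours apparent benefit.

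A reader might conclude that the plan does overstate day-7 improvement. The documents do not support that: they give no hospitalisation rate, and with no cases the bias is zero. With one case it is about 2 percentage points (1.8 from 35%, 2.4 from 45%). At the ceiling of four it is 8.8 or 11.3 points. These figures assume a completer analysis and that removed patients are true non-responders. The overstatement of the mean, 0.045 to 0.36 SD across the cases shown, applies to complete pairs. The random effects model removes it if removal follows the 24-hour score and only reduces it otherwise.

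This should be corrected before the data are analysed. It does not invalidate the study.

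**What to change.** Leave the clinical removal rule as it is.

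In Statistics:
- State the response criterion, and count patients removed for hospitalisation or worsening after infusion as non-responders at day 7 in all responder analyses. Patients hospitalised before infusion have no treatment outcome and should not be counted this way.
- Make the random effects model, with all observed scores, the analysis of day-7 change in place of the complete-pair t test.
- Add a worst-case sensitivity analysis for the missing day-7 scores.
- Define end point for the Kaplan-Meier analysis, and count hospitalisation for worsening as a relapse event only in patients who had already met the response criteria.

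In Protections against risk, item 9, separate stopping study procedures from collecting outcomes, so that the day-7 HDRS and MADRS are still obtained from patients who consent. This changes the participation wording, so it needs a small protocol and consent amendment as well as the additions to Statistics.

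The other costs are a slightly lower reported response rate if such cases occur and an occasional rating done in hospital.
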